NCT03724487

A COmmunity and Tech-Based ApproaCh for Hypertension Self-MANagement (COACHMAN)

Protocol 1.0

Sept 12, 2018

Introduction

Given the recently published criteria for hypertension (HTN), a blood pressure (BP) $>130/80$ mmHg, more Americans are likely to face the challenge of managing this chronic condition.¹ It is projected that HTN prevalence among U.S. adults will increase from 32% to 46%.² African Americans (AAs) are disproportionately affected by HTN when compared to all other racial-ethnic groups,³ and they experience greater disease severity (heart attack, stroke) compared to other racial-ethnic groups.^{3,4} Factors associated with nonadherence to HTN self-management include low income, limited access to health care, and or the lack of HTN knowledge.⁴⁻⁷ Substantial evidence has demonstrated the important role of community support in improving patients' management of chronic illnesses.⁸⁻¹¹ However, such community support programs rarely offer technology-based intervention (TBI) as a delivery method to improve HTN self-management.¹⁰

Therefore, this proposal constructs community partnerships with civic, health, and social organizations (Cleveland Council of Black Nurses and American Heart Association) to modify and evaluate TBI to promote medication adherence to antihypertensive therapy and improve BP control among AAs with HTN. *We propose to adapt and evaluate the efficacy of a multicomponent program for HTN self-management referred to as COACHMAN.* The proposed project has two phases: (1) a community engagement phase, and (2) a pilot evaluation phase. Consistent with the principles of community participatory action research,^{9,12} the project design will include having stakeholders provide feedback on the key feature of COACHMAN to enhance its feasibility and acceptability. In addition, we will generate data on the efficacy of the intervention that will inform stakeholders. We will gain information on how to allocate community resources to promote HTN self-management using technology, as well as provide data needed for future federal grant proposals. A series of informal sessions and qualitative interviews will be conducted with stakeholders and participants in phase one of the proposed project, and a pilot trial of COACHMAN will be conducted thereafter on AAs with HTN.

COACHMAN innovatively integrates TBI with community resources and enables participants to monitor their blood pressure, access web-based education, mobile application medication management, and receive exposure to behavioral counseling from community health worker to support self-managing their HTN.^{12,13} *Our central hypothesis* is that COACHMAN (evidenced-based strategies of HTN education, behavioral skills training, and social support) would be more effective than usual care at motivating AAs with HTN to improve BP control. A *secondary hypothesis* is that the COACHMAN intervention will result in improved BP control. Thus, the aims of this study are:

- Aim 1. Identify key content, design, and resources from a community of stakeholders, including determining facilitators and barriers of HTN management among AAs that will inform the development of COACHMAN using qualitative research methods.
- Aim 2. Evaluate the feasibility and acceptability of COACHMAN to improve BP control.
- Aim 3. Compare the difference in BP control between COACHMAN and EUC.

Impact: The long-term goal of this project is to generate evidence that will inform interventional research that reduces the cardiovascular disease risks and suboptimal or poor HTN self-management in this vulnerable AA population. Cleveland is ideal to conduct this research, as Ohio is ranked 15th nationally for prevalence of HTN, with even higher rates observed in AAs.¹⁴

A. RESEARCH STRATEGY

Significance. African Americans (AAs) have higher rates of hypertension (HTN) incidence, as well as cardiovascular disease (CVD) morbidity and mortality compared to all other racial-ethnic cohorts.¹⁻⁴ HTN is the most influential contributor to incidence of adverse CVD events.^{15,16} COACHMAN targets barriers to hypertension (HTN) knowledge, medication adherence, problem-solving skills, patient-provider communication, and social support in an effort to improve blood pressure (BP) control. If demonstrated to be effective, COACHMAN will be practical, scalable, and highly generalizable to a wide variety of individuals and serve as a linkage from community to clinic in the Cleveland area.

Barriers to BP control and HTN self-management are multifactorial. Poor adherence to anti-hypertensive therapy (AHT) is estimated to occur in 43-78% of patients prescribed AHT, with 50% discontinuation after a year, and notably worse and sooner in AAs.³ Recent research now recommends lower BP goals.^{17,18} Evidence suggests that inability to achieve BP control likely arises from a complex interaction of patient, provider, and system-level barriers.^{6,19} For this patient-focused project, the key barriers for BP control and HTN self-management are competing health priorities, lack of awareness of HTN knowledge, lack of confidence to self-manage HTN, depression, and lack of social support.²⁰

The use of technology for self-management of chronic disease is evolving.²¹ Contrary to the popular belief that AAs use less technology,²² AA smartphone use is 81% compared to 74% of the total population, and AAs spend close to 56 hours a month using apps or mobile Internet browsers on their smartphones.^{22,23} The proposed COACHMAN intervention represents a conceptual progression of the digital age and leverages technology for education and training, including the benefits of convenience, cost, and the ability to remotely deliver a highly focused, short-duration, HTN self-management intervention. Preliminary Work. In one study, our research team conducted a 90-minute focus group session to explore AAs' (N=21) experiences with using technology (mobile devices and apps) for HTN self-management.^{24,25} The majority of the participants owned smartphones and used this technology to communicate; seek, acquire, and share information; engage in entertainment; and organize and manage time. Participants expressed concerns about not being informed or trained to integrate technology for HTN self-management.²⁶

Community engagement in HTN self-management. Substantial evidence has demonstrated the importance of community support in improving patients' management of chronic illnesses.¹¹ Programs that incorporate multiple strategies such as involving prominent community members as well as trustworthy health educators and providing convenient, low cost, and culturally tailored interventions are more likely to engage AAs.^{11,27} Unfortunately, such programs rarely offer technology-based intervention (TBI) as a delivery method. We propose to evaluate the feasibility and acceptability of a TBI among AAs with HTN. PI [name] has already begun informal sessions with community partners (National Black Nurses Association and American Heart Association) as well as hypertension experts to develop this grant proposal and to obtain input to begin the initial design of the TBI for HTN self-management for AAs.

B. INNOVATION. Many communities have begun HTN screening or provider/system initiatives to improve BP control. However, such programs have not focused on effective patient engagement strategies with TBIs for self-managing HTN. This proposal addresses those gaps by leveraging

successful and replicable community programs with the addition of TBIs to advance the science of HTN self-management.

[figure not shown]

Figure 1: Conceptual Framework

C. APPROACH. A convenience sample of AAs with uncontrolled HTN will be conducted to obtain data on study variables and outcomes at baseline, 8 weeks, and 12 weeks. The primary outcome is change in BP from baseline to three months. A secondary outcome will be the proportion of participants achieving BP $< 130/80$ mm Hg at three months. Ryan and Swain's Individual and Family Self-Management

Theory,²⁸ (Figure 1) guides the major constructs of this study. Community stakeholders will be engaged throughout the project for continual input to refine and implement study intervention (see Statement of Work). The *initial phase* of this inquiry will begin by conducting informal sessions and focus groups to assess motivators as well as barriers to HTN management (Aim 1) followed by implementation of COACHMAN. [name] (Nursing Professor at Case Western Reserve University) has extensive expertise in community participatory research and will provide qualitative method support.

Study Intervention. The COACHMAN intervention is comprised of **four components**: 1) self-monitoring blood pressure (SMBP), 2) web-based education (adapted from the American Heart Association's Check, Change, Control),¹² 3) training/support for Medisafe application, and 4) nurse counseling. Study investigators will also use forged and ongoing relationships with the Cleveland Council of Black Nurses (CCBN) and other community partners to engage in all aspects of this study and serve as Community Health Workers (CHWs).¹⁰ The Enhanced Usual Care (EUC) group will receive one education session on SMBP and printed materials from the American Heart Association on "The Facts About High Blood Pressure" and the DASH Diet. All participants will receive study-provided automated home BP monitors (Omron 10 Series).

Setting and Sample. Given that this is a pilot study, a sample size of 40 is considered adequate. Participant inclusion criteria are as follows: (1) self-identifying as AA; (2) aged 30 years or older; (3) diagnosed with HTN (BP $\geq 140/90$ mm Hg) and taking at least one antihypertensive medication; (4) able to read/understand English; and (5) own a smartphone with a data plan, with the capability to download the Medisafe app and view videos. Exclusion criteria are: (1) history of cognitive impairment, and (2) currently using medication management app.

Recruitment and Retention. Various recruitment strategies such as fliers, brochures, and target ads through social media platforms (Facebook, ResearchMatch.org), as well as advertisements at community events and clinics,²⁹ will be used simultaneously. In addition, our community partners will assist recruitment. Our study population will be recruited from University Hospitals and from community outreach engagement. We anticipate limited difficulty in recruiting participants due to the [name] experience in clinical research and long-term working relationship with the participants and providers, as well as continued work with other cardiovascular trials. We will recruit three participants per week over a 4-month (December-April) period. While [name] has experience with recruiting and managing clinical trials, she is an Early Stage Investigator (without NIH grant awards) in her second year as an Assistant Professor (tenure track) in the School of Nursing at Case Western Reserve University.

Variable	Measure	Time of Measure		
		Baseline	8 Weeks	12 Weeks
Health Outcomes				
BP Change	BP <140/90 mmHg	X	X	X
Health-related QOL	PROMIS Global Health-10, ³⁰	X		X
Secondary Health Outcomes				
BP Control	At least 65% of participants with BP control<140/90 mmHg			X
Behavior Outcomes				
Medication Adherence	Hill-Bone Compliance Scale, ³¹	X	X	X
Patient Activation	Patient Activation Measure Short Form-PAM-13, ³²	X	X	X
Self-Management Outcomes				
HTN knowledge and Awareness	Hypertension Knowledge-Level Scale-HK-LS, ³³	X		X
Self-efficacy	Self-efficacy for Managing Chronic Disease, ³⁴	X		X
Technology Use	System Usability Scale-SUS, ³⁵		X	X
Technology Adoption	Mobile Application Rating Scale-MARS, ³⁶		X	X
Contextual Factors				
Demographics	Demographic Questionnaire	X		
Hypertension History	Charleston Morbidity Index, ³⁷	X		
Biometric Health Screening	Height and Weight, BMI, Kidney function, proteinuria	X		X
Social Support	Duke Subjective and Instrument Support, ³⁸	X	X	X
Spirituality	The Daily Spiritual Experience Scale, ³⁹	X	X	X
Depression	PROMIS Depression Scale-Short Form, ⁴⁰	X	X	X

Data Collection and Procedures. Study variables, measures, and data collection points are shown in Table 1 (page 5). After consent is obtained, participants will be randomized to COACHMAN or EUC with a 1:1 ratio. At baseline and 12 week visits, we will conduct biometric health screening test (height, weight, and blood samples). A trained RA will provide subjects assigned to COACHMAN a structured 30-minute training session on how to use study website and Medisafe on smartphone. For those subjects assigned to EUC, the RA will provide education materials. Follow-up phone sessions on medication adherence and additional training will be provided by the CCBN trained as CHWs.

Fidelity of the intervention “dose” (delivered, received, enacted) will be monitored regularly throughout the study by obtaining measures of subject responses to medication reminders, receipt of behavior change, and attendance to follow-up visits.

Statistical Analysis. For Aims 1 and 2, focus group sessions and key informant interviews will be transcribed verbatim and analyzed with NVivo 10 or a similar software package using principles of inductive content analysis. For Aim 3, the primary analysis compares BP levels between the COACHMAN intervention and the EUC group across three time points (baseline, 8, and 12 weeks). We will use a repeated measures analysis of variance (RMANOVA) built around a two group by three time points to assess mean differences across time, group differences, and the interaction of time X group.⁴²

Study Timeline. Months 1-2: Project start-up, finalize online web-based system, begin recruitment. Months 2-5: Recruitment, randomization, enrollment; begin intervention delivery; Months 3-9: Continue intervention delivery; data collection and system monitoring and retention; Months 9-12: Data cleaning, analysis, dissemination.

Potential Problems and Alternative Strategies. Due to the pilot nature of this study, each participant will be required to use their own data plan. As noted in preliminary studies, a majority of participants own or have cell phones in our qualitative study. Thus, we expect few exclusions related to cell phone ownership. Participants will receive a total of \$215, which is intended to cover any costs incurred from cell phone usage, and overall study participation. This pilot trial is intended to inform the design of a larger clinical trial, including its scalability, especially in terms of costs that are not more than we anticipate, or pose a problem for participant or retention. Future trials will provide study phones with prepaid data plans for those individuals with limited resources.

References

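### Two members of one household can enrol and be randomised to different arms; the likely dilution of the BP contrast is small, and one screening question prevents it

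*Combined protocol and SAP*

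**What the plan says.** All references are to the combined protocol and SAP.

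- **Eligibility (Setting and Sample).** There are five inclusion criteria, none about household. The exclusion list is complete in one sentence: "Exclusion criteria are: (1) history of cognitive impairment, and (2) currently using medication management app".
- **Recruitment (Approach; Recruitment and Retention).** This is a convenience sample. "Our study population will be recruited from University Hospitals and from community outreach engagement". The channels include fliers, social media and "advertisements at community events and clinics". The section adds: "In addition, our community partners will assist recruitment".
- **Allocation (Data Collection and Procedures).** "After consent is obtained, participants will be randomized to COACHMAN or EUC with a 1:1 ratio". No linked allocation or stratification by household is described.
- **Size (Setting and Sample).** "Given that this is a pilot study, a sample size of 40 is considered adequate". No alpha, power, effect size, SD or dropout rate accompanies the figure.
- **What differs between arms (Study Intervention; Data Collection and Procedures).** COACHMAN has self-monitoring of BP, web-based education, Medisafe training and support, and nurse counselling. Its participants get a "structured 30-minute training session on how to use study website and Medisafe on smartphone". EUC gets one session on self-monitoring plus printed materials. Every participant, in either arm, gets a home BP monitor.
- **Monitoring and analysis.** The fidelity plan tracks the dose of the intervention and names no measure of EUC exposure to COACHMAN. The primary analysis is a two-group by three-time RMANOVA with no household term. Potential Problems and Alternative Strategies deals with data plans, phone ownership and costs.

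**The concern.** Nothing in eligibility, allocation or follow-up prevents or records a household with one member in each arm. In such a household the EUC member has easy access to the website and to someone already trained on Medisafe, and can hear what was said in counselling. Every EUC participant must own a smartphone able to run Medisafe, so the means are there. The app exclusion helps only at entry: it bars a person already using a medication management app, but not one who starts after randomisation.

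Aim 3 and the primary outcome rest on the between-arm comparison of BP. Exposure of EUC participants moves their outcomes toward those of COACHMAN and biases the difference toward zero. No household link or exposure record is specified, so the team could not readily tell afterwards whether this had happened. The pilot is meant to inform a larger trial, so the same gap could carry forward.

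**Working it through.** The plan's own figure of 40 cannot be reproduced, because no inputs to a calculation are given. I take it as stated, with 20 per arm under 1:1 allocation.

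**Step 1. Chance that a co-enrolled pair is split.** With exactly 20 and 20 out of 40: 2 × 20 × 20 / (40 × 39) = 20/39 = 0.513.

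**Step 2. Expected share of the EUC arm exposed.** For k pairs: k × (20/39) / 20 = k/39. The documents give no value for k; I assume 1 to 4.

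**Step 3. Contrast retained.** Observed difference = true difference × (1 − h × s), where h is the share of EUC exposed and s is the fraction of the effect passed on. Neither is in the documents; s = 1 is the upper bound.

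| Pairs enrolled | Expected split pairs | Expected share of EUC exposed | Retained, s = 0.5 | Retained, s = 1 |
|---|---|---|---|---|
| 1 | 0.51 | 2.6% | 98.7% | 97.4% |
| 2 | 1.03 | 5.1% | 97.4% | 94.9% |
| 3 | 1.54 | 7.7% | 96.2% | 92.3% |
| 4 | 2.05 | 10.3% | 94.9% | 89.7% |

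These are averages over the randomisation. A single pair that is in fact split exposes 1/20 = 5% of the EUC arm.

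**Step 4. Size against the trial's precision (illustrative).** Assume two-sided alpha 0.05 and 80% power. The detectable difference with 20 per arm is (1.960 + 0.842) × √(2/20) = 0.886 SD, and the standard error is √(2/20) = 0.316 SD. If the true difference is 0.886 SD and s = 1:

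- One pair: bias 0.886 × 0.026 = 0.023 SD, about 7% of one standard error; power 77.9%.
- Three pairs: power 73.4%.
- Four pairs: bias 0.886 × 0.103 = 0.091 SD, about 29% of one standard error.

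The loss becomes large only for counts that seem unlikely among 40 people. Ten pairs with s = 1 would expose 25.6% of EUC and leave power at 54.9%.

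**Step 5. Non-independence.** Correlated outcomes within a household raise the variance of the arm difference when both members are in one arm (probability 19/39 = 49%) and lower it when they are split (51%). On average the two nearly cancel.

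**Step 6. Room to exclude.** Three recruits a week over four months (16 to 17.3 weeks) is 48 to 52 people against a target of 40.

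**The case against.** The strongest reply is that nothing in the documents suggests households will co-enrol. The sentence on community partners says only who helps with recruitment. Both members of a pair would have to self-identify as African American, be 30 or older, have hypertension on treatment, own a suitable smartphone with a data plan, and not be using a medication app. A reader might infer from the guiding individual-and-family theory that families will be recruited together. The plan uses that theory for its constructs, not as a recruitment scheme. This stands: the number of pairs is an assumption.

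A reader might also infer that the whole of COACHMAN is shared in a split household. It is not. Monitors go to everyone and EUC has a session on self-monitoring, so that component is not a contaminant. Training is given to the assigned participant and counselling is directed at a person, so a cohabitant gets it second-hand at most. Full spillover is therefore an upper bound.

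Nor do the documents support a claim that unmodelled household correlation invalidates the RMANOVA; Step 5 shows that it roughly cancels.

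Finally, exclusion is not the only remedy. Households could be allocated together, or links recorded and linked participants left out in a sensitivity analysis. That is fair. Allocating households together, however, would introduce clustering that the planned analysis does not model. What remains after all this is a gap in eligibility that is real, small in effect and cheap to close.

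**Conclusion.** The point holds as a minor improvement. The criteria and the individual 1:1 allocation permit a split household, and the plan neither prevents nor records it. The direction of bias is toward no difference. For 1 to 4 co-enrolled pairs under 20:20 allocation, the expected exposure is 2.6% to 10.3% of the EUC arm, and the expected shrinkage of the contrast is at most the same. This rests on assumed pair counts; the upper bound takes the full effect as passed on. A reader might conclude that the BP comparison is seriously compromised. The documents do not support that: they give no sign of how often households would enrol, and even four pairs at full spillover give an expected bias below a third of a standard error in the illustration.

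**What to change.** Add exclusion criterion (3) in Setting and Sample: lives in the same household as a person already enrolled in the trial. Ask it at screening, before randomisation.

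The cost is one line in the criteria and one screening question. The downside is that a few otherwise eligible people cannot join, which matters in a community-engaged study, although the planned recruitment rate leaves room for it. Individuals remain the unit of randomisation and analysis, so the RMANOVA needs no change.

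This closes only the household route. It does not address sharing among friends or members of the same community group, or an EUC participant who takes up Medisafe independently after randomisation.

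### Does Aim 2 (feasibility and acceptability) need a stated quantitative analysis in addition to content analysis of interviews?

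*Combined protocol and SAP*

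**What the plan says.** The list of aims gives Aim 2 as "Evaluate the feasibility and acceptability of COACHMAN to improve BP control". It attaches no measure, estimate or success threshold. The Statistical Analysis section covers Aim 2 together with Aim 1: "For Aims 1 and 2, focus group sessions and key informant interviews will be transcribed verbatim and analyzed with NVivo 10" or similar software, by inductive content analysis. The only other analysis in the document is the Aim 3 repeated measures ANOVA of blood pressure, with two groups and three time points.

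Several quantities that bear on feasibility or acceptability appear elsewhere:

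- **Accrual**, under Recruitment and Retention: "We will recruit three participants per week over a 4-month (December-April) period".
- **Fidelity**, under Data Collection and Procedures, monitored through "subject responses to medication reminders, receipt of behavior change, and attendance to follow-up visits".
- **Technology scales**, in Table 1: "System Usability Scale-SUS" and "Mobile Application Rating Scale-MARS", both at 8 and 12 weeks with no baseline.
- **Retention**, which appears as a section heading and a Study Timeline activity.

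Potential Problems and Alternative Strategies says the pilot should inform a larger trial, "including its scalability, especially in terms of costs that are not more than we anticipate, or pose a problem for participant or retention".

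**The concern.** A feasibility aim usually leads a statistician to look for numbers: how fast participants were recruited, how many stayed, how much of the intervention they used. Content analysis can explain barriers and describe acceptability, but it cannot supply a retention proportion or an accrual rate. The Aim 3 model cannot be stretched to cover the gap. It is confined to blood pressure and uses three time points, whereas SUS and MARS have two and no baseline, and accrual, retention and fidelity are not repeated scores of that kind.

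Read literally, then, Aim 2 could be reported with no estimate of uptake, use or retention, in a pilot whose purpose is to plan a larger trial. Because summaries and denominators are not fixed, they could also be chosen after the data are seen. For example, SUS could be reported among responders only, with or without the number of responders out of all those randomized to COACHMAN.

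**Working it through.** **1. Is the omission real?** Yes. The Statistical Analysis section holds two analyses, the content analysis and the blood pressure ANOVA. No other section states a summary, denominator or comparison for accrual, retention, fidelity, SUS or MARS. Monitoring fidelity during the trial is a commitment to collect it, not an analysis.

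**2. Does it contradict what Aim 2 promises?** No. The aim is worded as an evaluation, without a promised estimate. The Introduction links feasibility and acceptability to stakeholder feedback on the program's key features, and a qualitative method fits that use. Table 1 places SUS and MARS among the self-management outcomes, beside hypertension knowledge and self-efficacy. Treating them and the fidelity measures as Aim 2 endpoints is a reasonable inference, but the documents do not make it.

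**3. Is the gap specific to Aim 2?** No. Quality of life, medication adherence, patient activation, knowledge and self-efficacy also have no stated analysis. The section is simply short.

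**4. Accrual, the one item with a planned value.** Inputs: three per week and four months (Recruitment and Retention); 40 participants (Setting and Sample).

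- Weeks needed: 40 / 3 = 13.3.
- Weeks available: 4 × 365.25 / 12 / 7 = 17.4.
- Recruits at the planned rate: 3 × 17.4 = 52.
- Rate sufficient for 40: 40 / 17.4 = 2.3 per week.

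The plan is consistent and has slack. Setting observed accrual against it takes one division.

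**5. What would descriptive summaries deliver?** Allocation at 1:1 gives 40 / 2 = 20 per arm. The documents give no retention rates or SDs, so those below are assumptions.

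| Assumed retention, one arm | Exact (Clopper-Pearson) 95% CI |
|---|---|
| 14/20 (70%) | 45.7% to 88.1% |
| 16/20 (80%) | 56.3% to 94.3% |
| 18/20 (90%) | 68.3% to 98.8% |

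For a mean, the 95% half-width in SD units is t(0.975, n − 1) / √n:

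- n = 20: 2.093 / 4.472 = 0.468 SD.
- n = 16 (assumed completers): 2.131 / 4 = 0.533 SD.

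For reminder response averaged over participants, with an assumed SD of 15 to 35 percentage points, that is 0.468 × 15 = 7 to 0.468 × 35 = 16 points at n = 20, and 8 to 19 points at n = 16. The same SD multiples apply to mean SUS or MARS.

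These figures describe the precision of summaries the analysts could report. They do not show an error in the plan or that 40 is the wrong sample size.

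**6. Could a firmer specification be written from the documents?** Only in part. The number of follow-up visits is not given. If only the 8- and 12-week visits count, a participant's attendance can be just 0, 0.5 or 1, and attendance nearly duplicates retention. The number of reminders and the source of the response data are not stated, nor is how receipt of behavior change is recorded. The documents do not say whether SUS and MARS rate Medisafe or the study website. They do imply that app-related summaries belong to one arm: "A trained RA will provide subjects assigned to COACHMAN a structured 30-minute training session on how to use study website and Medisafe on smartphone".

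**The case for a change.** The strongest case for a change is that the pilot exists to inform a larger trial, that retention is named in that purpose, and that no sentence commits the investigators to report it or any other feasibility figure. A few descriptive lines would cost almost nothing, need no new visits, and settle denominators before the data arrive.

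The factual part of this stands: nothing in the document obliges the analysts to produce these summaries or fixes their form. The consequence is weaker than it sounds. Nothing bars descriptive reporting, and accrual and retention fall out of the enrollment and visit records. The scope for selective choice is modest, because instruments and visit times are already fixed and no test, threshold or go/no-go rule rests on the results. The added lines would also leave out cost, which the statement of purpose stresses, and could not define the reminder and visit denominators without information the documents lack.

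Timing might be raised as well. The Introduction and the Approach place the early qualitative work before the pilot, which would leave Aim 2 resting on pre-intervention views. That goes too far. The interviews in the Statistical Analysis section are undated, and the Approach promises stakeholder input throughout the project, so later interviews cannot be ruled out.

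**Conclusion.** No change is needed. The plan does not say how feasibility-related data will be summarized, but no stated rule or figure gives a wrong result, and the Aim 3 comparison is untouched. The gap is one that analysts fill sensibly: observed accrual against three per week, the proportion of those randomized with a 12-week blood pressure by arm, and mean SUS and MARS in COACHMAN with the number responding out of all randomized to that arm. At 20 per arm these would be planning figures of modest precision, for example 56% to 94% for an assumed 16/20 retained, and 0.47 SD either side of a mean with full response.

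The conclusion assumes that a pilot team reports such summaries as routine and that no progression decision is tied to them; the documents state none. If a formal go/no-go rule for the larger trial were to rest on these measures, their definitions and denominators would have to be fixed beforehand, and the gap would matter more.

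### The primary outcome is the three-month change in BP, but the primary RMANOVA names no deciding term, no 12-week group contrast and no primary BP component

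*Combined protocol and SAP*

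**What the plan says.** Section C (Approach) states: "The primary outcome is change in BP from baseline to three months". Aim 3 is "Compare the difference in BP control between COACHMAN and EUC". The Statistical Analysis section then sets the primary analysis for Aim 3 on BP levels at baseline, 8 and 12 weeks, not on changes, and specifies the model: "We will use a repeated measures analysis of variance (RMANOVA) built around a two group by three time points". The section gives the purpose of this model as "to assess mean differences across time, group differences, and the interaction of time X group".

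Nothing in the document says which of these terms decides Aim 3. No 12-week contrast, confidence interval or significance level is given, and BP is never resolved into a primary systolic or diastolic measure. In the table of measures, the BP Change row gives only a joint threshold, below 140/90 mm Hg, at all three visits. Baseline BP enters the model only as the first repeated level, not as a covariate.

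**The concern.** The stated outcome is a change to one time point and the stated aim is a comparison of arms. None of the three listed terms delivers that quantity directly.

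- **Time** is not a between-arm comparison.
- **Group** averages the arm difference over three visits. At one of them, baseline, randomization makes the expected difference zero.
- **Time by group** does test differential change, but as a two-degree-of-freedom omnibus test. It gives no 12-week estimate and can be significant because of week 8 alone.

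Two between-arm terms and two BP components leave four candidate answers, and the choice could be made after seeing the data. The trial also has a planning purpose: "This pilot trial is intended to inform the design of a larger clinical trial". The Introduction promises efficacy data as well. Both uses need one effect estimate with an interval, and the listed F tests do not supply it.

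**Working it through.** **Inputs from the document.** Total sample 40 (Setting and Sample), 1:1 allocation (Data Collection and Procedures), hence 20 per arm; visits at baseline, 8 and 12 weeks; entry BP at least 140/90 mm Hg.

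**Inputs assumed, because none is given.** SD 15 mm Hg at each visit, correlation 0.5 between visits, true 12-week difference 10 mm Hg, two-sided 5%, no dropout. The week-8 difference is 10 (full) or 5 (half).

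**The plan's own figure.** The sample size of 40 has no derivation to reproduce: "Given that this is a pilot study, a sample size of 40 is considered adequate". As a back-calculation only, 20 per arm gives 80% power for a standardized difference of (1.960 + 0.842) × √(2/20) = 0.89.

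**Dilution in the group term.** It estimates (0 + d8 + d12)/3. Full: (0 + 10 + 10)/3 = 6.7. Half: (0 + 5 + 10)/3 = 5.0. That is 2/3 and 1/2 of the 12-week effect.

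**Standard errors and noncentrality.**
- Group: variance of a person's mean = 225 × (1 + 2 × 0.5)/3 = 150; SE = √(2 × 150/20) = 3.87; 38 df.
- Interaction: λ = 10 × Σ(d − mean d)² / [225 × (1 − 0.5)]. Full: 10 × 66.67/112.5 = 5.93. Half: 10 × 50/112.5 = 4.44. F on 2 and 76 df under sphericity.
- 12-week change score: variance = 2 × 225 × (1 − 0.5) = 225; SE = √(0.1 × 225) = 4.74; 38 df.
- 12-week ANCOVA: SE = √(0.1 × 225 × 0.75 × 37/36) = 4.16; 37 df.

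**Power (group / interaction / change score / ANCOVA).**

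| Scenario | Full effect at week 8 | Half effect at week 8 |
|---|---|---|
| Closed form, no truncation | 39 / 56 / 54 / 65% | 24 / 44 / 54 / 65% |
| Simulated, systolic baseline cut at 140, source mean 135–145 | 57–63 / 62 / 60–61 / 64–65% | 36–41 / 48–49 / 60–62 / 65% |

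The second row allows for the entry criterion, since the sample is "A convenience sample of AAs with uncontrolled HTN". Simulations used 20,000 trials per scenario.

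The order of the terms depends on unknowns. With a full effect and no truncation, group v interaction power is 47% v 42% at correlation 0.3 and 33% v 79% at 0.7.

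**Disagreement.** Group and interaction differ on significance in 51% (full) and 47% (half) of simulated trials without truncation, and in 32–38% and 36–41% with it.

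**False positives with no true effect.** For two independent tests, 1 − 0.95² = 9.75%; simulated, 9.6%. For four independent tests, 1 − 0.95⁴ = 18.5%. Simulated over 40,000 trials with systolic–diastolic correlation 0.4 / 0.6 / 0.8, the rates are about 18% / 17% / 15%. One named contrast gives 5%.

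**Effect at week 8 only (10, then 0).** Here λ is again 5.93, so the interaction is significant in 56% of trials (59–61% with truncation), against 5% for the 12-week test.

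**Interval half-width.** Change score: 2.024 × 4.74 = 9.60 mm Hg. ANCOVA: 2.026 × 4.16 = 8.44, or 12% narrower. With truncation it is 8.6–8.8 v 8.4, only 3–5% narrower, and 1–2% at correlation 0.7.

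**The case against.** The strongest reply is that the Approach section already fixes the outcome as a change, and of the listed terms only time by group tests differential change. On that reading two candidates remain, systolic and diastolic, and the false-positive rate is about 10% at most. The reading is sensible, but the plan does not adopt it: group differences are listed within the primary analysis on equal terms. Even if it were adopted, the BP component and the 12-week estimate would still be undefined.

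Several further points stand in part:

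- The disagreement rates are not harm in themselves. The two terms test different hypotheses, so they will often differ. The rates matter only if either term may be reported as the answer.
- An effect that is complete at week 8 and gone by week 12 is a constructed case. It shows what the omnibus test can respond to, not what is likely.
- Omitting baseline as a covariate costs precision, not validity, and the entry criterion makes the cost small. With a full effect by week 8, ANCOVA has no power advantage over the interaction at correlations of about 0.75 or more. With a truncated baseline the crossover is about 0.7 (interaction 82–83%, ANCOVA 80–81%).
- RMANOVA software can produce the needed 12-week contrast with an interval. The plan simply does not ask for it.
- This is a pilot with no stated significance level or decision rule, so error control carries less weight. But the plan calls this its primary analysis and promises efficacy data, and a pilot's main product is an estimate with its uncertainty.

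**Conclusion.** The concern holds and should be fixed. The text alone settles the main point: the outcome is a three-month change, while the primary analysis names no deciding term, no 12-week between-arm contrast and no BP component. The dilution of the group term to 1/2–2/3 needs only the assumption that half to all of the 12-week effect is present at week 8.

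The power, half-width and disagreement figures rest on the assumed SD, correlation and effect, and would move with them. For example, with half the effect at week 8 and no truncation, an SD of 12 to 18 takes interaction power from 63% to 32% and ANCOVA power from 83% to 50%. The gain from the change is chiefly one defined 12-week estimate; added precision is modest. The model itself is not invalid.

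**What to change.** Add to the Statistical Analysis section: *The single primary result is the 12-week between-group difference in [one named BP component, for example systolic], adjusted for baseline BP, with a 95% confidence interval.* Obtain it in one of two ways:

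- ANCOVA on the available 12-week readings; or
- a mixed model of the 8- and 12-week readings with baseline BP, group, visit and group by visit, using a small-sample degrees-of-freedom correction.

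Treat week 8, the other BP component and the RMANOVA terms as supportive.

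If the team wants RMANOVA as its only model, the minimum repair is to name the group contrast in 12-week-minus-baseline BP, for one component and with its 95% interval, as the one primary result.

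In either case, reconcile the BP Change row of the measures table, which now shows a threshold, with the continuous outcome.

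The cost is one or two sentences plus the table entry; no new data, visits or participants. The downsides are slightly more modelling and, for the mixed model, few participants from whom to estimate the covariance parameters.
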